476 experience. This will examine relevant core constructs of trust, acceptance, satisfaction,
477 confidence as well as fear, worries, distress and burden. Validated and reliable measures will be
478 used to explore psycho-behavioral characteristics and outcomes in addition to specifically
479 adapted measures for SAM and DSS technologies to capture holistic, disease-specific and
480 technology-specific data. These questionnaires will evaluate how specific constructs are
481 predictive of successful glycemic outcomes associated with DSS. These questionnaires will enable
482 us to assess important non-glycemic treatment outcomes that are meaningful to patients
483 including those affecting Quality of Life (QOL) (e.g. fear of hypoglycemia and diabetes distress).
484 To those ends, participants will complete a battery of questionnaires related to diabetes
485 management, treatment satisfaction and QOL at baseline (before system use) and after each
486 treatment modality.

487 **1.3.5. Ecological Momentary Assessment Data Collection**

488 Participants will be trained on the EMA surveys and requirements. During each treatment
489 condition, over the course of 2-3 days every two weeks, the participant will be asked to complete
490 a "Daily Diary" with 3-5 entries of 3-4 questions each day, for a minimum total of 48 entries per
491 participant during each Phase. The DiAs phone will display a text message containing a link to the
492 survey. Surveys will be triggered at fixed times, including a morning survey ~1h after waking up
493 and an end-of-the-day survey around 8-9 PM. Participants will be able to delay (up to 30 min) or
494 skip (up to 2 per day excluding at wake up) surveys for their convenience. Participants will
495 respond to questions on a 5-point Likert scale (0=Not at All, 4=Extremely). The first Diary for each
496 day will contain two additional items for rating sleep quantity/quality. The Daily Diary questions
497 are intended to assess agreement, trust, treatment satisfaction, diabetes burden, self-efficacy,
498 mood valence, energy level, physical well-being, and concerns about hypo- and hyperglycemia.
499 The first Diary for each day will contain two additional items for rating sleep quantity/quality.

CLINICAL PROTOCOL

500 **1.3.6. Mapping of Psycho-behavioral Characteristics to DSS Preferences and Performance**

501 Baseline assessments of psycho-behavioral traits will be introduced as covariates in the general

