502 linear model when analyzing the glycemic performance of each treatment modality (SAM, PF,
503 DSS). Contrasts will be used to study each pair, specifically SAM vs any advisory system. For
504 constructs that can be changed by the intervention itself (e.g. Fear of hypoglycemia) and that are
505 therefore measured after each intervention, we will use repeated measures model with within-
506 subject covariates (MIXED models) to understand their impact on DSS efficacy. This analysis will
507 shed light on the relationship between the efficacy of treatment modality and individual patient
508 characteristics; **Aims 2.1 and 2.2**

509 Using the cloud data system, we will isolate patient-system interactions for each advisory module
510 (e.g. eA1c, predictive hypoglycemia alert), and compute for each subject the probability of the
511 interaction to lead to the expected action, and positive glycemic outcomes. These probabilities
512 will then be used as outcome variables in separate analysis to assess whether psycho-behavioral
513 traits are associated with the acceptance of specific advisory functionalities (e.g. Fear of
514 Hypoglycemia could be lowered by the hypoglycemia prediction module); answering **Aim 2.3**.

515 **1.3.7. Identification and Validation of the Acceptance & Trust Index**

[figure not shown]
516 Finally, we will use the validated trust and acceptance measures obtained throughout the
517 protocol to validate the dynamic tracking of ATI. The 80 studied subjects will be divided in 4
518 cohorts of 20, the first 3 groups used to iteratively refine our estimation procedure (interaction
519 quantification and dynamical model parameters) to accurately reproduce acceptance and trust
520 fluctuations. The last group will be used to prospectively demonstrate the correlation between
521 ATI, trust, and acceptance, thereby addressing **Aim 3.2**; retrospectively we will use the finalized
522 method on all 80 participants to compute the auto-correlation between trust and acceptance
523 and ATI and study the ability of ATI to track changes in time; **Aim 3.3**. Such an index, shown to
524 follow the evolution of robustly assessed trust and acceptance (via standard methods) will enable
525 future systems to characterize its interactions with its user, detecting early drop in adherence
526 and disconnect with patient's expectation (fault detection), and potentially associating them with

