670 evaluations are available, a decision will be made to determine the participant's eligibility for the
671 study or if one or more parts of the screening will have to be repeated. If at the first screening or
672 repeat screening an exclusionary condition is identified, the participant will be excluded from
673 participation with follow up and referred to their primary care physician as needed. The study
674 physician may elect to rescreen participants and collect additional laboratory values if their
675 clinical situation changes.

676 **3.5. Post-screening assessments**

677 If the subject is deemed eligible to participate in the study, the subject will elect to use either
678 continuous subcutaneous insulin infusion (CSII) or MDI therapy for the duration of the study, no
679 changes are allowed during the study. Furthermore, the participant will elect to use
680 carbohydrates counting or not for the computation of the meal bolus, this choice will apply to
681 the entire study.

682 Participants will then go through a baseline psycho-behavioral assessment. The following
683 questionnaires will be completed:

- 684 • Diabetes Specific Personality Questionnaire
- 685 • ABACUS
- 686 • Diabetes Locus of Control
- 687 • Confidence in Diabetes Self-Care Scale
- 688 • Clarke's Hypoglycemia Awareness Scale Participant Inclusion Criteria
- 689 • Demographic Data Survey (screening visit only)

690 **Chapter 4 Training Visit**

691 Participants may use CSII or multiple daily insulin (MDI) injection therapy for their diabetes
692 management. Participants will be asked to maintain this treatment throughout the study. In the
693 event that MDI participants elects to change to CSII therapy (see section 3.5), the run-in period
694 will include a period of insulin stabilization for up to 6 weeks. The study physician may elect to
695 extend this time frame if additional time would be beneficial to the participant.

696 If participants intend on identifying carbohydrate counting (carbohydrate ratio, insulin sensitivity
697 factor and glucose goal) at mealtime, they will be asked to continue to provide this information
698 throughout the study.

699 **4.1. Visit 2 - Study Equipment**

700 **4.1.1. Study Continuous Glucose Monitor Training**

701 A Dexcom G6 CGM will be provided to all participants at the training session. The participants
702 will be provided with CGM equipment and instructed to use the study CGM on a daily basis. If

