- **Insulin on Board:** Tracks active insulin to avoid insulin stacking using a common 4-6 hour
871 action curve.
- 872
- **Personalized weekly feedback.** Provides advice to the user on what went well in terms
873 of glycemic control and system use in the past week and what may be a good thing to
874 focus on for the following week.

875 **6.4.2. Phase 2 Initiation Questionnaires**

876 Participants randomized to escalation will complete the following questionnaires:

- 877
- Technology Expectations (burdens subscale only)
- 878
- INSPIRE (revised for DSS)

CLINICAL PROTOCOL

879 **6.4.3. Adverse Event Assessment**

880 The participant will be asked about any of adverse events, adverse device effects, and device
881 issues since the last visit. The participant will also be asked if there were any low BGs <54 mg/dL,
882 high BGs >300 mg/dL, or ketones ≥ 3.0 mmol/L since the last visit.

883 Once all training activities are completed, the participant will be given adequate supplies and
884 study devices to last until the subsequent clinic visit. An appointment for Visit 5 will be scheduled.
885 Participants will be encouraged to contact the study team between visits as needed (i.e. report
886 adverse events in real-time).

887 **6.5. Home Use of DiAs in Phase 2 Mode**

888 The participant will complete a minimum of 8 weeks of DiAs use in Phase 2 Mode at home.

889 During the course of Phase 2, participants will complete EMA surveys and post-phase
890 questionnaires.

891 **6.5.1. Phase 2 EMA Surveys**

892 Over the course of 2-3 days every two weeks of Phase 2, the participant will be asked to complete
893 a "Daily Diary" with 3-5 entries of 3-4 questions each day, for a minimum total of 48 entries per
894 participant during each Phase.

895 **6.5.2. Post-Phase 2 Questionnaires Week 7**

896 All participants will be sent the following questionnaires on week 7 (day 42 of Phase 2) and will
897 be asked to complete them within 1 week:

- 898 • Technology Acceptance (burdens subscale only)
- 899 • Pittsburgh Sleep Quality Index
- 900 • T1-Diabetes Distress Scale

901 **6.5.3. Post-Phase 2 Questionnaires Week 8**

902 All participants will be sent the following questionnaires on week 8 (day 49 of Phase 2) and will
903 be asked to complete them within 1 week:

- 904 • Hypoglycemia Fear Survey
- 905 • Hyperglycemia Avoidance Scale
- 906 • Confidence in Diabetes Self-Care Scale

CLINICAL PROTOCOL

907 **6.6. Visit 5 – Phase 3 Initiation**

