1122 Participants randomized to de-escalation will complete the following questionnaires:

- 1123 • ABACUS

1124 **7.8.2. Adverse Event Assessment**

1125 The participant will be asked about any of adverse events, adverse device effects, and device
1126 issues since the last visit. The participant will also be asked if there were any low BGs <54 mg/dL,
1127 high BGs >300 mg/dL, or ketones ≥ 3.0 mmol/L since the last visit.

CLINICAL PROTOCOL

1128 **7.9. Post Study Check-In Visit (Visit 7)**

1129 Approximately 48 hours after the home use of the equipment, the study team will contact the
1130 participant via phone/email/text to assess:

- 1131 • Adverse events, adverse device effects, and device issues
1132 • Blood glucose values <60 mg/dL and >300 mg/dL

1133 **Chapter 8 Testing Procedures**

1134 **8.1. Laboratory / Point of Care Testing**

1135 **8.1.1. HbA1c**

- 1136 • A blood sample will be obtained at screening to obtain a baseline hemoglobin A1c level.
- 1137 • HbA1c level may be measured by study team using the DCA2000, a comparable point of
1138 care device, at time of screening
- 1139 • Labs may be obtained at a local laboratory (e.g. LabCorp) convenient to the participant.
- 1140 • Blood test may be obtained within 14 days prior to enrollment may be used for eligibility
1141 purposes.
- 1142 • Sample collected at randomization and end of study will be used for statistical purposes.

1143 **8.1.2. Comprehensive Metabolic Panel**

- 1144 • A blood sample will be obtained at screening to assess kidney and liver functioning.
- 1145 • Labs may be obtained at a local laboratory (e.g. LabCorp) convenient to the participant.
- 1146 • Blood test may be obtained within 14 days prior to enrollment may be used for eligibility
1147 purposes.

1148 **8.1.3. Thyroid Stimulating Hormone**

- 1149 • A blood sample will be obtained at screening to assess thyroid function.
- 1150 • Labs may be obtained at a local laboratory (e.g. LabCorp) convenient to the participant.
- 1151 • Blood test may be obtained within 14 days prior to enrollment may be used for eligibility
1152 purposes.

1153 **8.1.4. Pregnancy Test**

1154 A blood/urine pregnancy test will be required for women of childbearing potential at the
1155 screening visit, and between each phase . Tests must be negative to participate in the study.

1156 **Chapter 9 Questionnaires & Ecological Momentary Analysis**

1157 **9.1. Diabetes Specific Personality Questionnaire**

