Week 7 of DiAs Use in Phase 3 Mode	Technology Acceptance (burdens subscale only) to assess patients' experienced burdens related to the use of DSS Pittsburgh Sleep Quality Index (PSQI) to assess whether DSS improves sleep quality and quantity.	Pittsburgh Sleep Quality Index T1-Diabetes Distress Scale
Week 8 of DiAs Use in Phase 3 Mode	Hypoglycemia Fear Survey Hyperglycemia Avoidance Confidence in Diabetes Self-Care Scale	Hypoglycemia Fear Survey Hyperglycemia Avoidance Scale Confidence in Diabetes Self-Care Scale
Visit 6 Study Exit	ABACUS INSPIRE (revised for DSS) Diabetes Locus of Control	ABACUS

1285

1286 **Chapter 10 Risks, Benefits, and Risk Assessment**

1287 **10.1. Potential Risks and Benefits of the Investigational Device**

1288 Risks and Benefits are detailed below. Loss of confidentiality is a potential risk; however, data are
1289 handled to minimize this risk. Hypoglycemia, hyperglycemia and ketone formation are always a
1290 risk in participants with T1DM and participants will be monitored for these symptoms.

1291 **10.1.1. Venipuncture Risks**

1292 A hollow needle will be placed in the arm for taking blood samples. Blood draws can cause some
1293 common reactions like pain, bruising, or redness at the sampling site. Less common reactions
1294 include bleeding from the sampling site, formation of a small blood clot or swelling of the vein
1295 and surrounding tissues, and fainting.

1296 There is the risk of contamination from blood sampling techniques. Hand washing with either
1297 soap & water or waterless hand sanitizer will be used prior to caring for the study subject. Gloves
1298 will be worn during blood sample collection and processing. Medical personnel will continue to
1299 practice hygiene for the subject's protection (i.e. hand washing, changing gloves frequently,
1300 disposing needles properly). Gloves will be removed and hands washed or sanitized prior to
1301 leaving and upon return to the subject's room. Soiled linen will be changed to minimize the
1302 transfer of pathogenic organisms.

1303 **10.1.2. Fingertick Risks**

1304 About 2 drop of blood will be removed by fingertick for measuring blood sugars and sometimes
1305 HbA1c or other tests. This is a standard method used to obtain blood for routine hospital
1306 laboratory tests. Pain is common at the time of lancing. In about 1 in 10 cases, a small amount of
1307 bleeding under the skin will produce a bruise. A small scar may persist for several weeks. The risk

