1620 **Chapter 13 Miscellaneous Considerations**

1621 **13.1. Prohibited Medications, Treatments, and Procedures**

1622 Participants using glulisine at the time of enrollment will be asked to contact their personal
1623 physician to change their prescribed personal insulin to lispro or aspart for the duration of the
1624 trial.

1625 The study devices (study insulin pump, study CGM) must be removed before Magnetic Resonance
1626 Imaging (MRI), Computed Tomography (CT) or diathermy treatment. Participants may continue
1627 in the trial after temporarily discontinuing use if requiring one of the treatments above.

1628 **13.2. Participant Withdrawal**

1629 Participation in the study is voluntary. Participant may withdraw at any time. For participants
1630 who do withdraw from the study, the study team will determine if their data will be used in
1631 analysis.

1632 **13.3. Confidentiality**

1633 For security and confidentiality purposes, subjects will be assigned an identifier that will be used
1634 instead of their name. Protected health information gathered for this study may be shared with
1635 the third-party collaborators. De-identified subject information may also be provided to
1636 collaborators involved in the study after the appropriate research agreement has been executed.

1637 **Chapter 14 Statistical Consideration**

1638 **14.1. Design and Randomization**

1639 This is a randomized crossover study in T1DM designed to demonstrate the efficacy of
1640 personalized feedback (PF) and decision support (DSS) over sensor-augmented pump (SAM)
1641 therapy and to establish relationships between the level of glucose variability (GV) control
1642 achievable by the intervention and individual psycho-behavioral characteristics.

1643 We plan to split the study into 4 cohorts of about 25 participants each (expected retention 20
1644 per cohort). Each cohort will continue for ~7 months and will have the structure presented in
1645 Figure 5. Following recruitment, screening, and a run-in period of SAM, participants will be
1646 randomized into one of two groups: escalation vs. de-escalation of devices and function. Each
1647 treatment modality (SAM, PF, DSS) will continue for about 8 weeks, with the last 4 weeks used
1648 to assess GV from CGM data.

1649 **Escalation: SAM → PF → DSS**

1650 **De-escalation: DSS → PF → SAM**

1651 **14.2. Sample Size**

1652 **14.2.1. Sample Size Determination:**

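### Diabetes Locus of Control is scheduled after PF and after DSS in both sequences but never after SAM, so the scale has no SAM score to compare with

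*Combined protocol and SAP*

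**What the plan says.** Section 14.1 defines two sequences: "Escalation: SAM → PF → DSS" and "De-escalation: DSS → PF → SAM".

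Section 1.3.4 states the general timing of the questionnaires. Participants complete a battery on diabetes "management, treatment satisfaction and QOL at baseline (before system use) and after each" treatment modality. Sections 1.3.3 and 14.4 present it as a strength of the design that one can explore the psycho-behavioral effect of adding features, restricting them, or taking them away (SAM). Section 14.5 plans to analyse the battery scores for change over time and between groups, with group and study phase in the model. Section 1.3.6 adds a mixed model with within-subject covariates for constructs that the intervention can change.

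Diabetes Locus of Control is first given at screening. Section 3.5 introduces that list with "Participants will then go through a baseline psycho-behavioral assessment. The following". For the two visits that follow SAM:

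- Section 6.4.2 (escalation, Visit 4) opens "Participants randomized to escalation will complete the following questionnaires" and lists only Technology Expectations and INSPIRE.
- Section 7.8.1 (de-escalation, Visit 6) opens "Participants randomized to de-escalation will complete the following questionnaires" and lists only ABACUS.

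By contrast, the escalation exit cell of table 9.13, which follows DSS, reads "ABACUS INSPIRE (revised for DSS) Diabetes Locus of Control".

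**The concern.** Section 9.3 describes the scale as measuring personal beliefs about control over one's diabetes management and its outcome. It does not ask about a device, so it can be answered after SAM as readily as after PF or DSS. Leaving out Technology Acceptance after SAM has an obvious reason. The documents give none for leaving out this scale.

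Two uses of the scale are at stake. As an outcome, it cannot show whether beliefs about control differ between SAM and an advisory mode. In de-escalation the last score is taken at Visit 5, before SAM begins, so the effect of removing the features is never observed on it. As a within-subject covariate, it is missing in every SAM period. The only score outside an advisory mode is Visit 1, which precedes the study system and always comes first.

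**Working it through.** No figure in the plan needs reproducing; the check is on the schedule and on what it allows to be estimated.

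**Step 1: where the scale is given.** The chapter text and table 9.13 agree in every cell.

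| Time | Escalation | De-escalation |
|---|---|---|
| Visit 1 (3.5) | given | given |
| Last week of run-in; Visit 3 (5.2.2, 6.2.2, 7.2.2) | not given | not given |
| Visit 4, after Phase 1 | after SAM: **not given** (6.4.2) | after DSS: given (7.4.2) |
| Visit 5, after Phase 2 | after PF: given (6.6.2) | after PF: given (7.6.2) |
| Visit 6, after Phase 3 | after DSS: given (6.8.1) | after SAM: **not given** (7.8.1) |

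The week 7 and week 8 lists in the SAM phases (6.3.2, 6.3.3, 7.7.2, 7.7.3) do not contain it either.

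**Step 2: count.** Sequences with a post-modality score: PF 2 of 2, DSS 2 of 2, SAM 0 of 2. With 80 expected completers (14.2.1), that is 0 of 80 after SAM. By phase, escalation has scores after Phases 2 and 3 and de-escalation after Phases 1 and 2. The group-by-phase analysis in 14.5 therefore has both groups only after Phase 2, when both are on PF.

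**Step 3: what can be estimated as scheduled.** Write each score as subject effect + modality effect (S, P, D for SAM, PF, DSS) + phase effect (π1, π2, π3). The within-subject differences available are:

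- Escalation, Visit 6 − Visit 5 = (D − P) + (π3 − π2)
- De-escalation, Visit 4 − Visit 5 = (D − P) + (π1 − π2)

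S appears nowhere, so D − S and P − S are not estimable, with or without phase terms. Entering Visit 1 as a level of its own does not change this. The mean of the two lines is (D − P) + (π1 + π3)/2 − π2, so even D − P needs a model without free phase terms.

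**Step 4: can Visit 1 stand in for SAM?** Only by relabelling. Visit 1 precedes the study CGM, pump and DiAs and comes first for everyone. In escalation it lies at least 2 + 8 + 8 = 18 weeks before the post-PF score (shortest run-in plus two phases). In de-escalation it lies at least 2 + 8 = 10 weeks before the post-DSS score. The result would be a before/after comparison, which randomizing the order does not protect.

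**Step 5: with the form added at the two post-SAM visits.**

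- DSS versus SAM. Escalation, Visit 6 − Visit 4 = (D − S) + (π3 − π1). De-escalation, Visit 4 − Visit 6 = (D − S) + (π1 − π3). The mean is D − S; the phase effects cancel.
- PF versus SAM. Escalation, Visit 5 − Visit 4 = (P − S) + (π2 − π1). De-escalation, Visit 5 − Visit 6 = (P − S) + (π2 − π3). The mean is (P − S) + π2 − (π1 + π3)/2, so free phase effects do not cancel.

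A rank check on the design matrix (subject and modality effects, with and without phase terms) gives the same answers. Post-SAM coverage goes from 0 of 2 to 2 of 2.

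**The case against.** A reader might infer that the plan commits itself to a Locus of Control contrast against SAM, and that this contrast is lost. The documents do not support that. The sentence in 1.3.6, "Contrasts will be used to study each pair, specifically SAM vs any advisory system", follows directly on the plan to enter baseline traits as covariates when analysing glycemic performance. The contrast is on glycemic outcome, and the Visit 1 score, taken in everyone, still serves it. No sentence names a modality contrast on this scale.

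It can also be said that 1.3.4 is a general statement. The personality questionnaire and the hypoglycemia awareness scale are given only at Visit 1, and ABACUS only at Visit 1 and exit, so the sentence cannot mean every form after every modality. The model with within-subject covariates in 1.3.6 gives fear of hypoglycemia as its example, not this scale. The omission after SAM is the same in both sequences, so it may be deliberate. The escalation versus de-escalation exploration is described as unpowered.

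All of this limits the point, but it does not explain the schedule. The scales given only at Visit 1 are not repeated after any modality. Locus of Control is repeated after two of the three. Hypoglycemia fear, hyperglycemia avoidance, diabetes distress, self-care confidence and sleep quality are all collected in the SAM phase of both sequences. If this scale is only a baseline trait, repeating it after PF and DSS has no stated purpose.

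The limits of the remedy also stand. PF versus SAM stays tied to phase because PF is always Phase 2, and that comes from the design. The plan describes no washout between phases, so a post-SAM score in de-escalation may carry over beliefs formed under DSS and PF.

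**Conclusion.** The gap is real and narrow. Followed as written, the schedule yields 0 of 80 post-SAM scores on one secondary scale. That scale cannot then be compared between SAM and PF or DSS as an outcome, nor used as a within-subject covariate in the SAM period. Its use as a baseline covariate for the glycemic contrasts is intact. The primary outcome (CV), Aim 1 and the sample size do not depend on it.

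The conclusion assumes that the schedule is followed as written. That the scale is meant to be able to change with treatment is inferred from its being repeated, together with the general aims in 1.3.3, 1.3.4, 14.4 and 14.5; the plan does not say so directly. Cheap improvement; low-to-moderate priority.

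**What to change.** Add Diabetes Locus of Control to 6.4.2 (escalation, Visit 4) and 7.8.1 (de-escalation, Visit 6), and to the matching cells of table 9.13. Use the post-SAM score, not Visit 1, as the SAM comparator. State in 14.5 that the DSS versus SAM comparison can be made with or without phase terms, and that PF versus SAM rests on a model without free phase effects.

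The cost is one 18-item form of about 5 minutes (9.3), once per participant, at visits that already give questionnaires. The downside is that small added burden. A post-SAM score cannot be recovered once a participant has moved on from that visit, so the change is worth making early.

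If the omission is intended, a sentence is enough: the scale is compared only between PF and DSS, and is otherwise a baseline covariate.
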